# 9.5 **Procedures for Reporting Adverse Events**

Adverse events that are ongoing at the end of the study visit will be followed. Phone calls will be placed with any subject who experiences an adverse event until the issue is resolved or the condition is considered ongoing and stable.

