9.2 Missing or Inconclusive Data Handling

Partial/missing start and end dates for AEs and concomitant medications required to flag data as treatmentemergent or concomitant with treatment will be imputed as follows:

Partial/missing start date:

- Dates with missing day only will be imputed as the 1st of the month unless the month and year are same as the month and year of first dose of study medication, in which case missing day will be imputed as the first dose day of study medication.
- Dates with both day and month missing will be imputed as 1 Jan unless the year is same as the year of first dose of study medication, in which case missing day and month will be imputed as the first dose day and month of study medication.
- Completely missing dates will be imputed as the first dose date of study medication unless the end date is on or before the first dose date of study medication, in which case missing date will be imputed as 1 Jan of the same year as the end date.

Partial/missing end date:

- Dates with missing day only will be imputed as the last day of the month unless the month and year are the same as the month and year of the last dose of study medication, in which case missing day will be imputed as the last dose day of study medication.
- Dates with both day and month missing will be imputed as 31 Dec unless the year is same as the year of the last dose of study medication, in which case missing day and month will be imputed as the last dose day and month of study medication.
- If the ongoing flag is missing or "Yes" then the date will not be imputed unless death date is available, in which case the missing date will be imputed as the death date. If ongoing is "No" then the missing end date will be imputed as the last dose date.
- If the imputed date is after the date of death, then the end date will be set equal to the date of death.

The original dates will be displayed in data listings and the imputed dates will be used in derivations only (study day, treatment-emergence status, etc).

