16.1 Adverse Events

For the purposes of this trial, an AE is defined as any untoward medical event occurring after the subject's signing of the informed consent until they are exited from the trial. An AE can therefore be any unfavorable and unintended sign, symptom, or disease occurring after the subject started the clinical trial, without any judgment about causality. Any pre-existing medical condition that worsens during the trial will also be considered a new AE. Documentation regarding the AE should be made as to the nature, date of onset, end date, severity, relationship to study procedure, expectedness, action(s) taken, seriousness, and outcome of any sign or symptom observed by the investigator or reported by the patient upon indirect questioning.

All AEs will be coded using the MedDRA Version 23.1.

Treatment-emergent adverse events (TEAEs) are defined as any event that occurs or worsens on or after the day that randomized study treatment is initiated. Adverse events recorded in the eCRF which began prior to treatment will not be included in the summary tables but will be included in the AE data listings.

An overall summary will be presented that includes the number and percentage of subjects who experienced at least one AEs, ocular AEs, non-ocular AEs, SAEs, AEs by maximal severity, AEs by relationship to study procedure, AEs leading to treatment discontinuation, and AEs resulting in death by treatment arm for the Safety Population. In addition, overall TEAEs and the number and percentage of subjects who experienced at least one TEAE, ocular TEAEs, non-ocular TEAEs, TE-SAEs, TEAEs by maximal severity, TEAEs by relationship to study procedure, TEAEs leading to treatment discontinuation, and TEAEs resulting in death by treatment arm for the Safety Population.

Separate summaries will be provided for the following categories of AEs:

- Ocular AEs by SOC and PT
- Non-ocular AEs by SOC and PT
- Ocular TEAEs by SOC and PT
- Non-ocular TEAEs by SOC and PT
- Instillation Site Ocular TEAEs by Duration of Time
- Ocular TEAEs by SOC, PT, and maximal severity
- Non-ocular TEAEs by SOC, PT, and maximal severity
- Ocular TEAEs by SOC, PT, and strongest relationship to study procedure
- Non-ocular TEAEs by SOC, PT, and strongest relationship to study procedure
- Ocular TEAEs by SOC, PT, maximal severity, and strongest relationship to study procedure
- Non-ocular TEAEs by SOC, PT, maximal severity, and strongest relationship to study procedure

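### SAP 9.2 sets some missing adverse-event end dates to the last-dose date with no lower bound, so an event can be ended too early or, after early stopping of dosing, before it began

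*SAP*

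**What the plan says.** SAP 9.2 handles adverse events and concomitant medications under one set of rules, for dates "required to flag data as treatmentemergent or concomitant with treatment will be imputed as follows". For end dates:

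- Day missing: the last day of the month is used, unless the month and year match the last dose, "in which case missing day will be imputed as the last dose day of study medication".
- Day and month missing: 31 December is used, unless the year matches the last dose, when the last-dose day and month are used.
- No date: "If the ongoing flag is missing or 'Yes' then the date will not be imputed unless death date is available". When the flag says the event is over, "then the missing end date will be imputed as the last dose date".
- An imputed end after death is moved back to the date of death.

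The section adds that "the imputed dates will be used in derivations only (study day, treatment-emergence status, etc"; original dates stay in the listings.

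Three other places bear on this. Protocol 9.5 states "Adverse events that are ongoing at the end of the study visit will be followed", by telephone, until the event resolves or is stable. The visit schedule in the Protocol synopsis and section 8.3.1 puts the final dose and study exit on the same day, Day 2, for completers. SAP 16.1 lists a summary titled "Instillation Site Ocular TEAEs by Duration of Time", which appears as Table 14.3.4.

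**The concern.** The last-dose date is a natural default for deciding whether a medication overlapped treatment. It says little about when an adverse event ended. Telephone follow-up exists because some events outlast the final visit, and an end date recalled by telephone may well be imprecise. The rule then returns the event to the last-dose day, ignoring what the site recorded afterwards.

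The section is also asymmetric. The rule for a completely missing start date checks the end date first, but no end-date rule checks the start date. Nothing stops an imputed end from falling before the event began.

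At stake are the derived end days of these events and, if the duration summary uses imputed dates, the description of how long local reactions to the drops last. No efficacy result is involved.

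**Working it through.** The plan gives no figure to reproduce. The check applies the SAP 9.2 rules to constructed cases.

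**Inputs.** The end-date rules are those of SAP 9.2. The no-date rule is read as covering completely missing dates, since the two rules before it cover partial ones. Last dose and exit on Day 2 for completers come from the Protocol visit schedule. Adverse events are collected from consent to exit (Protocol 9.1, SAP 16.1). Under the early-termination text in Protocol 8.3.1, the safety evaluations may be done on the day of discontinuation or when the investigator chooses, so exit can fall on a later day than the last dose.

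**Assumptions.** Day 1 = 9 Nov 2021 and Day 2 = 10 Nov 2021, for illustration only. Duration in days = end - start + 1, because the readable SAP gives no formula.

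| Case | Start | Last dose | End-date information | Imputed end | Duration |
|---|---|---|---|---|---|
| A. Completer, ongoing Yes or flag missing | 9 Nov | 10 Nov | none | none | not derived |
| B. Completer, starts on Day 2 after the last dose, ongoing No | 10 Nov | 10 Nov | none | 10 Nov | 10 - 10 + 1 = 1 |
| C. Completer, present at exit, truly resolved 17 Nov, ongoing No | 10 Nov | 10 Nov | none, or Nov 2021 | 10 Nov | 1; true value 17 - 10 + 1 = 8 |
| D. Completer, resolved the following month | 10 Nov | 10 Nov | Dec 2021 | 31 Dec | 21 + 31 = 52 |
| E. Dosing stopped on Day 1, event starts on Day 2, ongoing No | 10 Nov | 9 Nov | none | 9 Nov | 9 - 10 + 1 = 0 |
| F. Dosing stopped on Day 1, event starts three days later, before exit | 12 Nov | 9 Nov | Nov 2021 | 9 Nov | 9 - 12 + 1 = -2 |
| G. Dosing stopped on Day 1, event present at exit on Day 2, later ongoing No | 9 Nov | 9 Nov | none | 9 Nov | 1; at least 10 - 9 + 1 = 2 |

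**Reading the cases.** In C the event is ended on the day it was recorded as present, the earliest end compatible with the record. In G it is ended a day before it was last seen. In E and F it ends before it starts. A and B show where the rule does no such harm, and D shows that SAP 9.2 can also give a long duration.

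**Effect of a lower bound** at the later of the start date and the last date recorded as ongoing: E moves to 10 Nov (1 day), F to 12 Nov (1 day) and G to 10 Nov (2 days). C stays at 1 day if exit is the last record of the event as present. If a call k days after exit recorded it as still present, C becomes k + 1 days. The bound therefore removes contradictions with the record, but it does not recover an unknown duration. That is why the duration table needs its own statement.

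**The case against.** The strongest reply is that the section is not about duration. Its stated purpose is flagging treatment-emergent events and concomitant medications, and the derivations it names are study day and treatment emergence. No readable text gives a formula, unit, categories or data source for Table 14.3.4, and some of this may be redacted. This stands: an effect on that table is conditional. The open-ended list does not exclude duration, however, and study day, which is named, already takes the wrong date.

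Several stronger readings are tempting but unsupported:

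- *Every event ongoing at exit is cut at the last dose.* It is not. A flag of Yes, or a missing flag, blocks imputation except to a death date. Only events later recorded as ended are affected.
- *Completers can have an end before onset.* By calendar date they cannot, because last dose and exit share Day 2 and adverse events are collected only until exit.
- *The section always shortens events.* Case D shows otherwise, and a missing start day in the first-dose month is moved to the first-dose day, which can lengthen an event.
- *End dates never bear on treatment emergence.* The rule for a completely missing start date depends on the end date.
- *Month-end imputation should replace the same-month exception.* In case C with Nov 2021 reported it would give 30 - 10 + 1 = 21 days against a true 8. That exchanges one arbitrary bound for another.

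It is also fair to say that telephone contact makes a wholly unknown end date less likely, that the same rule applies in both arms, and that original dates remain in the listings. These points limit the effect but do not justify an end date that contradicts the record.

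**Conclusion.** The point holds as a small defect in a stated rule. SAP 9.2 can end an adverse event on the last-dose day although the site knew it lasted at least until then or longer. For a subject who stopped dosing early, it can end the event before it began. The first needs an event later recorded as ended with a missing or matching partial date. The second also needs an onset on a calendar day after the last dose and before exit.

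The documents give no count of such events. With two days of dosing and only incomplete end dates at issue, few are likely. The durations of 1, 0 and -2 days rest on assumed dates and an assumed formula; they show how the rule works and do not estimate its impact. A reader might infer that Table 14.3.4 understates how long local reactions last. The readable text does not establish this, because it does not say that the table uses imputed dates.

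**What to change.** Add one sentence to SAP 9.2: an imputed adverse-event end date may not be earlier than the event's start date or the last date on which the event was recorded as ongoing. The existing upper bound at death can stay, and the medication rules need no change.

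Add one sentence to SAP 16.1: Table 14.3.4 uses observed durations only, or marks any duration that rests on an imputed date. This covers completers in case C, where the lower bound alone may leave the end date at Day 2.

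The cost is two sentences and minor programming, and a few durations become longer. If telephone-contact dates are not available for analysis, which the readable documents do not settle, the last date recorded as ongoing falls back to the exit visit.

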9.3 Definition of Baseline

Baseline is defined as the last measurement prior to the first dose of study treatment,

Change from baseline will be calculated as post-baseline measurement – baseline measurement.

9.4 Data Analysis Conventions

All data analysis will be performed by SDC after the study is completed and the database has been locked and released for unmasking. Statistical programming and analyses will be performed

All statistical tests will be

Unless otherwise specified, summaries will be presented by treatment group and, where appropriate, visit. Listings will be sorted by subject number, visit/time point, and parameter as applicable.

9.5 Adjustments for Multiplicity

Step	Endpoint	Allocated Two- sided Alpha Level

Disposition of Subjects

Subject disposition will be presented in terms of the numbers and percentages of subjects who were randomized who were included in the following analysis populations: ITT, PP, and Safety; and who completed the study and discontinued from the study. Subjects who are not discontinued from the study will be considered study completers. Disposition will be summarized by treatment group and for all subjects. Percentages will be calculated using randomized subjects as the denominator unless otherwise specified.

The reasons for premature study discontinuation will be summarized by treatment group for all discontinued subjects. Percentages will be calculated using discontinued subjects as the denominator. The reasons for study discontinuation that will be summarized include AE(s), protocol violation(s), administrative reasons, Sponsor termination of study, subject choice, and other. COVID-19 related discontinuations will be summarized similarly by treatment group as well. A subject listing will be provided that includes the date of discontinuation, reason for study discontinuation, and an indication of COVID-19 relatedness with a description.

The number and percentage of subjects with any deviation, major deviation, and minor deviation will be summarized by treatment group for all randomized subjects. The protocol deviations that will be summarized include the following categories:

A subject listing will be provided that includes the visit, date of the deviation,

the deviation category, the deviation description, and the classification of whether the deviation was judged to be major or minor in a masked review.

Subject listings will be provided that include randomization information such as randomization number, treatment group, and date. Listings will also be provided to include subject data for inclusion and exclusion criteria violations and exclusions from the study populations.

11. Demographic, Previous Participation in Reproxalap Trials, and Pretreatment Variables

11.1 Demographic Variables

The demographic variables collected in this study include

Subjects who record

Age (years) will be summarized, overall and by treatment, using continuous descriptive statistics. Age will also be categorized Age will be reported in years and calculated using the following formula:

Age = (Informed Consent Date – Date of Birth) / 365.25, truncated as an integer

The number and percentage of subjects will be presented,

A subject listing that includes all demographic variables, including informed consent, will be provided.

11.2 Previous Participation in Reproxalap Trials

The number of subjects and percentages of subjects that dosed with randomized study drug in previous Reproxalap trials will be summarized by treatment group and for all subjects in the ITT population.

Subjects who did not dose under previous Reproxalap studies will be summarized as well.

11.3 Pretreatment Variables

All baseline efficacy and safety variables will be summarized by eye (or subject level) by treatment group and all randomized subjects.

Quantitative variables will be summarized by using descriptive statistics with qualitative variables summarized by counts and percentages. Summaries will be provided of the ITT and Safety Populations.

12. Medical History and Concomitant Medications

12.1 Medical History

Medical history will be coded using Medical Dictionary for Regulatory Activities (MedDRA) Version 23.1.

Listings of medical history will be generated separately for

12.2 Concomitant Medications and Procedures

Concomitant medications and procedures will be coded using World Health Organization Drug Dictionary (WHODrug) and summarized to the therapeutic drug class

and preferred name. If the second s

then the next lowest classification that is provided in the coding dictionary will be used. The preferred name will be defined as the active ingredient; if the active ingredient is not provided or includes more than two ingredients (e.g., multivitamins), then the drug name will be summarized as the preferred name. Any uncoded terms will be summarized under the

Concomitant medications are defined as those medications listed as having been taken (1) prior to initiation of study drug administration and continuing for any period of time following the first administration of study drug or (2) at any time following the first administration of study drug. Prior medications are defined as those medications as having been taken prior to initiation of study drug administration but not continuing any time following the first administration of study drug.

Concomitant medications will be summarized . Medications will be tabulated for each treatment group using frequencies and percentages.

At each level of subject summarization, a subject will be counted once if he/she reports one or more medications. Percentages will be based on the number of subjects in each treatment group. Listings of concomitant medications will be generated separately for ocular and non-ocular data.

13. Dosing Compliance and Treatment Exposure

13.1 Dosing Compliance

Dosing compliance will be assessed by calculating the number of actual doses received and comparing that to the number of expected doses as follows:

The number of actual doses received will be calculated from in-office instillation eCRF page.

Dosing compliance (%) will be summarized

The compliance category defined above will be summarized with discrete

summary statistics.

A subject listing of dosing compliance will also be produced.

13.2 Treatment Exposure

Extent of treatment exposure for subjects who complete the study or those that discontinue the study

Extent of treatment exposure for each subject exposed to study drug will be summarized with continuous descriptive statistics for each treatment group A subject listing of treatment exposure will also be produced.

14. Efficacy Analyses

All efficacy analyses described in this section will have

14.1 Primary Analysis

The primary endpoint will be deemed to have been met if any of the 3 assessments that comprise the primary endpoint are achieved, as is described

14.1.1 OVERALL MEAN CHANGE FROM BASELINE OF CONJUNCTIVAL REDNESS DURING THE CAE AT VISIT 3 (DAY 2)

These average scores for each separate eye will be used for analysis of the overall mean change from baseline of conjunctival redness.

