# **1** INTRODUCTION

#### **STUDY OBJECTIVES** 2

To evaluate the efficacy of reproxalap, as assessed by conjunctival redness, Schirmer's Test, and ocular dryness Controlled Adverse Environment®

(CAE) in subjects with dry eye disease.

#### **CLINICAL HYPOTHESES** 3

The clinical hypothesis is that reproxalap is more effective than vehicle in reducing the signs and symptoms of DED.

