#### **10.2 Statistical Hypotheses**

The following hypothesis will be tested comparing reproxalap to vehicle. The null hypotheses must be rejected for the dosing regimen to claim efficacy.

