#### **10.4 Statistical Analysis**

#### 10.4.1 General Considerations

[figure not shown]
Quantitative variables will be summarized descriptively using number of subjects (n), mean, standard deviation, median, minimum, and maximum. Qualitative variables will be summarized using counts and percentages.

All summaries will be presented by treatment group. Summaries will be provided for demographics, baseline medical history, concurrent therapies, and subject disposition.

[figure not shown]

The statistical analysis plan (SAP) will detail the statistical procedures, and will dominate any text herein.

[figure not shown]

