This SAP is being written with due consideration of the recommendations outlined in the most recent International Conference on Harmonisation (ICH) E9 Guideline entitled Guidance for Industry: Statistical Principles for Clinical Trials, E9(R1) Statistical Principles for Clinical Trials: Addendum: Estimands and Sensitivity Analysis in Clinical Trials and the most recent ICH E3 Guideline entitled Guidance for Industry: Structure and Content of Clinical Study Reports.

This SAP describes the data that will be analyzed and the subject characteristics, efficacy, and safety assessments that will be evaluated. This SAP provides details of the specific statistical methods that will be used. The statistical analysis methods presented in this document will supersede the statistical analysis methods described in the clinical protocol. If additional analyses are required to supplement the planned analyses described in this SAP, they may be completed and will be identified in the clinical study report.

2. Study Objectives

To evaluate the efficacy of reproxalap, as assessed by conjunctival redness, tear RASP levels, Schirmer's Test, and symptoms after dosing prior to and during exposure to the Controlled Adverse Environment[®] (CAE) in subjects with dry eye disease.

3. Study Endpoints

3.1 **Primary Endpoint**

The primary efficacy endpoint is comprised of the following:

Conjunctival redness
Visual analog scale (VAS)
Schirmer's test

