14.1.1.1 MIXED MODEL REPEATED MEASURES USING SCORES FROM EACH EYE

Overall mean change from baseline
will be compared between reproxalap and vehicle.

Protocol ADX-102-DED-024 SAP, Version 1.0

met, then the trial will have been deemed to have been successful in demonstrating sign activity of reproxalap.

To examine the robustness of the redness analysis, the following additional sensitivity analyses will be executed:

Subjects will be asked to rate eye dryness

	A subject listing of the eye dryness during the CAE will be generated.
14 1 2 1	
14.1.2.1	ADDITIONAL SENSITIVITY ANALYSES
14 .1.3 Mea	N CHANGE FROM BASELINE OF UNANESTHETIZED SCHIRMER'S TEST
Unanesthetiz	zed Schirmer's test will be assessed for each eye.
14.1.3.1	MIXED MODEL REPEATED MEASURES USING SCORES FROM EACH EYE
Mean CFB o	of unanesthetized Schirmer's test
	A subject listing of the unanesthetized Schirmer's test will be generated.

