16.5 Intraocular Prossuro (IOP)	

16.5 Intraocular Pressure (IOP)

Subjects' IOP will be assessed		
	. A sub	ject listing of IOP will also be produced.

17. Changes from Protocol-Stated Analyses

No changes to protocol-stated analyses will be executed.

18. References

No references cited.

19. Revision History

Documentation of revision to the SAP will commence after approval of the final version 1.0.

20. Tables

Tables (10 tables) in **boldface** font will be delivered in topline package.

Table Number Title Population	pulation
---------------------------------------	----------

	Subject Disposition	All Screened	
Table 14.1.1		Subjects	
Table 14.1.2.1	Demographics	ITT Population	
Table 14.1.2.2	Demographics	Safety Population	
Table 14.1.2.3	Previous Participation in Reproxalap Trials	ITT Population	
Table 14.1.3.1	Baseline Disease Characteristics	ITT Population	
Table 14.1.3.2	Baseline Disease Characteristics	Safety Population	
Table 14.1.4.1	Ocular Medical History	ITT Population	
Table 14.1.4.2	Non-Ocular Medical History	ITT Population	
Table 14.1.5.1	Ocular Concomitant Medications	ITT Population	
Table 14.1.5.2	Non-Ocular Concomitant Medications	ITT Population	
	Overall Mean Change from Baseline of	ITT Population with	
	Conjunctival Redness (Ora Calibra [®] Scale)	Observed Data	
Table 14.2.1.1		Only	
	Overall Mean Change from Baseline of Conjunctival	PP Population with	
	Redness (Ora Calibra [®] Scale)	Observed Data Only	
Table 14.2.1.2			
	Overall Mean Change from Baseline of Conjunctival	ITT Population with	
	Redness (Ora Calibra [®] Scale)	Observed Data Only	
Table 14.2.1.3			
	Overall Mean Change from Baseline of Conjunctival	ITT Population with	
	Redness (Ora Calibra [®] Scale)	Observed Data Only	
Table 14.2.1.4			
	Overall Mean Change from Baseline of Conjunctival	ITT Population with	
	Redness (Ora Calibra [®] Scale)	PMM	
Table 14.2.1.5			
	Overall Mean Change from Baseline of Conjunctival	ITT Population with	
	Redness (Ora Calibra [®] Scale)	MCMC	
Table 14.2.1.6			
	Overall Mean Change from Baseline of Eye	ITT Population with	
	Dryness (Visual Analog Scale)	Observed Data	
Table 14.2.2.1		Only	

	Overall Mean Change from Baseline of Eye Dryness	PP Population with
Table 14.2.2.2	(Visual Analog Scale)	Observed Data Only
	Overall Mean Change from Baseline of Eye Dryness	ITT Population with
Table 14.2.2.3	(Visual Analog Scale)	PMM
	Overall Mean Change from Baseline of Eye Dryness	ITT Population with
Table 14.2.2.4	(Visual Analog Scale)	MCMC

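### Does Protocol 10.2 demand more for an efficacy claim than the any-of-three success rule in SAP 14.1?

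*SAP*

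**What the plan says.** - **SAP 3.1** treats the primary endpoint as one endpoint with three parts ("The primary efficacy endpoint is comprised of the following"): conjunctival redness, dryness VAS and Schirmer's test. Two are signs and one is a symptom.
- **SAP 14.1** gives the decision rule: "The primary endpoint will be deemed to have been met if any of the 3 assessments that comprise the primary endpoint are achieved". The sentence then runs into removed text.
- **SAP 14.1.1.1**, on redness, keeps the end of a conditional whose start is removed: "then the trial will have been deemed to have been successful in demonstrating sign activity of reproxalap".
- **SAP 9.5** has a table with columns for step, endpoint and allocated two-sided alpha. Its rows are not visible.
- **Protocol 10.2** begins "The following hypothesis will be tested comparing reproxalap to vehicle" and continues "The null hypotheses must be rejected for the dosing regimen to claim efficacy". The hypotheses are not visible.
- **Protocol 3** states the clinical hypothesis that "reproxalap is more effective than vehicle in reducing the signs and symptoms of DED".
- **Protocol 10.4.1** settles precedence: "The statistical analysis plan (SAP) will detail the statistical procedures, and will dominate any text herein". The protocol synopsis and SAP 1 say the same in substance.
- **SAP 17** states: "No changes to protocol-stated analyses will be executed".

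**The concern.** Read quickly, the two documents seem to hold different success rules. The plural in Protocol 10.2 suggests that the whole set of nulls must fall before efficacy is claimed, while SAP 14.1 is satisfied by one. If so, the SAP has relaxed the protocol's rule and SAP 17 should have said so, because the protocol synopsis commits the SAP to recording changes to protocol-stated analyses.

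There is also a question of scope. The clinical hypothesis covers signs and symptoms. Under SAP 14.1, a win on Schirmer's alone, or on dryness alone, counts as the primary endpoint met. If that result were presented as support for the full hypothesis, one domain would be claimed without evidence. The choice of rule also affects the chance of success considerably, so a real discrepancy would matter.

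**Working it through.** **1. Is there a contradiction in the visible text?**

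| Question | Protocol 10.2 | SAP 14.1 |
|---|---|---|
| How many hypotheses? | Singular in the lead-in, plural in the next sentence | Three assessments |
| How many must be rejected? | Not stated; neither *all* nor *any* appears | Any one |
| Claim named | Efficacy, with no domain | Primary endpoint met |
| Text removed nearby | The hypotheses; also 10.4.4 (multiplicity) and most of 10.4.5 (primary analysis) | The end of the sentence |

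A contradiction needs the protocol to require all three. It does not visibly do so, and the sections where it would state its rule are redacted. SAP 17 therefore cannot be called false. The reference to signs and symptoms comes from Protocol 3, which states a general hypothesis and not a decision rule. No visible sentence joins it to the condition in 10.2.

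**2. Which rule will be run?** Any-of-three, under the precedence statements in both documents.

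**3. Is any-of-three acceptable for error control?** No alpha allocation is fully visible, so there is no plan figure to reproduce. As an illustration with independent tests, the chance of at least one false win is 1 − Π(1 − αᵢ):
- unadjusted: 1 − 0.95³ = 14.3%;
- equal thirds of 0.05: 1 − (1 − 0.0167)³ = 4.9%;
- an assumed 0.001/0.001/0.048 split: 1 − 0.999² × 0.952 = 5.0%. (The value 0.001 appears twice in the protocol synopsis under multiplicity, but the endpoints it belongs to are not visible.)

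At correlation 0.9, simulation gives 8.4%, 3.0% and 4.8% respectively. If the allocated alphas sum to 0.05, the rule holds the family-wise error at or below 5% whatever the correlation.

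**4. How far apart would the two rules be?** Inputs: n = 75 per arm (Protocol 4); effect d in SD units, assumed equal on all components; independent tests. Power for one component is p = Φ(d√(n/2) − z), with √(75/2) = 6.124, z = 1.960 at 0.05 and z = 2.394 at 0.05/3. Any-of-three uses the split alpha. All-of-three uses 0.05 for each test, since a rule that requires every test to win needs no split.

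| d | p at 0.05 | p at 0.0167 | Any: 1 − (1 − p)³ | All: p³ |
|---|---|---|---|---|
| 0.3 | 0.451 | 0.289 | 64% | 9% |
| 0.4 | 0.688 | 0.522 | 89% | 33% |
| 0.5 | 0.865 | 0.748 | 98% | 65% |

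Correlation narrows the gap. At d = 0.4, simulation gives 82% against 40% at correlation 0.3, and 74% against 48% at 0.6.

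**5. How often would the endpoint be met without a win in both domains?** At d = 0.4 with equal thirds and independence, dryness plus at least one sign wins with probability 0.522 × (1 − 0.478²) = 0.403. The shortfall from any-of-three is 0.891 − 0.403 = 49%. By simulation it is 40% at correlation 0.3 and 29% at 0.6. One-domain success is a likely outcome under these assumptions, so how it is reported matters.

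**6. Does the plan let such a result pass as a two-domain claim?** Nothing visible does. The redness section confines its success statement to sign activity. The estimand in SAP 3 gives a separate population-level summary for each component. The table list in SAP 20 gives each its own primary results table (14.2.1.1, 14.2.2.1 and 14.2.3.1). A reader of the results will see which component won.

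**The case for a change.** The best argument for a change is that precedence settles only which rule is run. A reader of the protocol alone cannot learn that one component suffices. The natural reading of a plural with no qualifier is that the set must be rejected, and even a lenient reading leaves 10.2 short of stating the SAP's rule. The limit to sign activity is visible only under redness, with no matching limit visible for Schirmer's or dryness. The edit would cost a few sentences and leave sample size and alpha untouched.

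Part of this stands. The wording of 10.2 is loose, its shift from singular to plural looks like a drafting slip, and step 5 shows that a one-domain win is not a remote case. The rest depends on treating redacted text as absent. The success sentence in SAP 14.1 is cut off, and most of the decision text for dryness and Schirmer's is removed. The missing limits may be there, so their absence from the public copy is no defect. Requiring one sign and one symptom for a combined conclusion would add a claim rule that no visible decision rule contains. That is a matter of preference in a Phase 2 trial.

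**Conclusion.** The concern does not call for a change. Any-of-three is a defined rule, it governs under both documents, and it sits beside an alpha allocation. Aligning the wording of Protocol 10.2 would alter no test, threshold or result.

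The large differences in power (89% against 33% at 0.4 SD under independence) would matter only if the protocol required all three wins, and the visible text does not say so. The effects, correlations and alpha splits used here are assumptions; none comes from the documents.

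Two small points remain: 10.2 does not visibly say how many nulls must be rejected, and the visible text states the scope of a single win only for redness. Analysts would fill both sensibly, running the SAP rule and claiming efficacy only for the component that won. Two things cannot be checked in the public copy: whether the allocated alphas in SAP 9.5 sum to 0.05, and whether the redacted hypotheses already match SAP 14.1. If the unredacted protocol did require all three rejections, SAP 17 would need correcting and this conclusion would change.
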